### **5.1.1 Study duration per subject**

For adult subjects, treatment will continue for at least 2 years. Once 2 years of participation are reached, adult subjects will continue to participate until 1 of the 2 following conditions are met.

- LCM is approved for use for the treatment of PGTCS in subjects with IGE in the subject's country for or until the latest approval is granted either by EMA, FDA, or PMDA.
- For pediatric subjects, treatment will continue until 1 of the following 2 conditions are met:

- up to 5 years of participation or
- until the approval of the extension of indication to cover the target age group is granted

Adult and pediatric subjects are completers if they continue in the study for the maximum duration in their respective region.

The following study periods are defined:

- A Treatment Period lasting for at least 5 years (238 weeks) for the population less than 18 years old at enrollment and will be shorter for adults leaving the study when the PGTCs indication approvals are being obtained during the course of the study.
- An up to 4-week Taper Period and a 30-day Safety Follow-Up Period.
  - Subjects continuing LCM treatment with commercially available LCM will transition to a dose determined by the investigator and do not have to perform the tapering (Taper Visit and SFU).
  - Subjects tapering off LCM will do so over a period of up to 4 weeks (see taper schedule, [Table 7–2](#)).
  - An End of Taper Visit (latest 3 days after the final dose) will occur after the final LCM dose for subjects who taper off LCM. Following the End of Taper Visit, there will be a 30-day Safety Follow-Up Period. The Safety Follow-Up Period consists of a clinic visit 2 weeks after the End of Taper Visit followed by a Safety Follow-Up telephone contact 30 days after the last dose of study drug. The same design will apply to some of the subjects tapered in SP0982 at the time of the 125th event and who entered EP0012 for the Safety Follow-Up Visit only and to subjects who entered EP0012 for a Safety Follow-up Visit after discontinuing SP0982 due to the study stopping.

The end of the study is defined as the date of the last visit/telephone contact of the last subject in the study.

Subjects who entered EP0012 as <18 years and become adults ( $\geq 18$  years) during the study, will remain in the study for at least 5 years (238 weeks).

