Year of study	Year 3			Year 4		Year 5 + Extended Period						
Visit c	TC d	V12	V13	V14	V15	V16	V17	Vx f	ET Visit g	Term Visit h	LCM Solution Dispensation Visit i	Unscheduled Visit
Week		118	142	166	190	214	238	X				NA
Concomitant medications and AED(s)	X	X	X	X	X	X	X	X	X	X		X
Physical exam (complete) j			X		X		X	X (odd visits only)	X	X		
Neurological exam (brief) k		X		X		X	X	X (even visit only)	X	X		
12-lead ECG l			X		X		X	X (odd visits only)	X	X		
Vital signs (BP and pulse) including orthostatic assessments m		X	X	X	X	X	X	X	X	X		X
Body weight and height n		X	X	X	X	X	X	X (even visits only)	X	X		
Tanner Stage o			X		X		X	X (odd visits only)	X	X		
Laboratory tests		X		X		X	X p	X p	X	X		
Endocrinology q									X	X		
Pregnancy test r		X	X	X	X	X	X	X	X	X		

**Table 5–2: Schedule of study assessments for Years 3 through 5 for EP0012 (Treatment Period, ET Visit, Termination Visit, and Unscheduled Visit for subjects <18 years at enrollment)**

	Treatment period a								End of Study period			Unscheduled b
Duration	Open-label: up to approximately 5 years								Up to 5 weeks			
Year of study	Year 3			Year 4		Year 5 + Extended Period						
Visit c	TC d	V12	V13	V14	V15	V16	V17	Vx f	ET Visit g	Term Visit h	LCM Solution Dispensation Visit i	Unscheduled Visit
Week		118	142	166	190	214	238	X				NA
Call IRT		X	X	X	X	X	X	X	X	X		X
C-SSRS s		X	X	X	X	X	X	X	X	X		X
Dispense subject diary		X	X	X	X	X	X	X	X	X		
Subject diary return/review		X	X	X	X	X	X	X	X	X		X
Dispense LCM		X	X	X	X	X	X	X	X	X	X	
LCM review/return		X	X	X	X	X	X	X	X	X	X	
Withdrawal criteria	X	X	X	X	X	X	X	X	X	X		X
AE reporting	X	X	X	X	X	X	X	X	X	X		X
Achenbach CBCL l			X		X		X	X (odd visits only)	X	X		
BRIEF u			X		X		X	X (odd visits only)	X	X		

AE=adverse event; AED=antiepileptic drug; BP=blood pressure; BRIEF=Behavior Rating Inventory of Executive Function; BRIEF-P=Behavior Rating Inventory of Executive Function-Preschool Version; CBCL=Child Behavior Checklist; C-SSRS=Columbia-Suicide Severity Rating Scale; ECG=electrocardiogram; ET=early termination; exam=examination; IRT=interactive response technology; LCM=lacosamide; NA=not applicable; Term=Termination; V=Visit; Vx=Visit X

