Note: Subjects who turn 18 years during the course of this study will be considered as pediatrics, however these subjects will not need to complete the Achenbach CBCL and BRIEF assessments.

- a The duration of the Treatment Period will vary by subject age group and is defined in Section 5.1.1.
- b Unscheduled Visits may be performed at any time after Visit 1 as clinic visits or telephone contacts, at the discretion of the investigator. In addition to the required assessments listed above, depending on the type of visit (clinic or telephone), further assessments can be completed as needed and may include physical or neurological examination, ECG, laboratory tests, etc. The C-SSRS must be performed if the Unscheduled Visit is due to a psychiatric AE.
- c A window of  $\pm 7$  days relative to Visit 1 is applicable for all visits and telephone contacts. Subjects will have a Telephone Contact every 8 weeks if no clinic visit is scheduled.
- d Telephone contacts are required every 8 weeks during the study. Telephone contacts are not required during weeks in which a clinic visit is planned (eg, Week 118). Therefore, telephone contacts are scheduled for: Year 3 - Week 102, Week 110, Week 126, Week 134; Year 4 - Week 150, Week 158, Week 174, Week 182; Year 5 - Week 198, Week 206, Week 222, Week 230. If the subject remains in the study beyond Week 238, telephone contacts will continue at 8-week intervals.
- e At the completion of the study, investigators should discuss treatment options with the subject and/or legal representative to best manage the subject's epilepsy.
- f Subjects may require additional routine visits (Visit X) if the study is still ongoing at Week 238 for the respective subject. Vx visits are to be performed every 24 weeks. Additional routine visits should be scheduled and performed in accordance with footnote 'b' to avoid visit window deviations. Assessments must be performed in accordance with Table 5-3.
- g An ET Visit must be completed for all subjects who prematurely discontinue from the study. This will be followed by LCM taper, an End of Taper Visit, and a Safety Follow-Up Period; see Table 5-4. For subjects who continue on commercial LCM, the early Termination Visit is the last visit in the study.

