- h A Termination Visit must be completed for all subjects who complete the study. This can be performed in alignment of the date of the last scheduled visit if appropriate. For subjects who will not continue on LCM, this visit will be followed by LCM taper, an End of Taper Visit, and a Safety Follow-Up Period; see Table 5-4. For subjects who continue on LCM, the Termination Visit is the last visit in the study.
- i Dispensation Visit will occur 12 weeks after each 24-weekly visit from Year 2 (Visit 11) to Year 3 onwards and will be for the purpose of dispensing LCM solution for pediatric subjects <50kg.
- j The complete physical examination will include cardiac and respiratory function via auscultation and review of all body systems.
- k The brief neurological examination will include selected assessment of general neurological status, reflexes, muscle strength, and coordination/cerebellar function.
- l The ECG recordings should be performed at the same time of day (when possible) and prior to blood sample collection and vital sign assessments. Care should be taken to assure proper lead placement and quality ECG recordings. If possible, subjects should rest in a supine position at least 5 minutes prior to each recording and should be motionless during the recording. In pediatric subjects (<18 years of age) a 12-lead ECG (2 interpretable recordings) approximately 20 to 30 minutes apart must be performed.
- m Blood pressure measurements should be taken with the proper placement and proper sized cuff to obtain accurate measurements.
- n Height will be recorded at Visits 12, 14, 16, Visit X (even visits), and at the ET and Termination Visit.
- o The Tanner Stage will be performed only for subjects who are pubescent at Visit 1 or who enter puberty during the course of the study.
- p Laboratory tests are applicable for combined the last scheduled visit/Termination Visit. If the last scheduled visit is not the Termination Visit, laboratory tests are not required.

- q If the patient was treated in SP0982, endocrinology should be done if age was <18 years at SP0982 Visit 1. If the patient was a Baseline failure in SP0982, endocrinology should be done if age is <18 years at EP0012 Visit 1.

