- r Pregnancy tests will be performed for female subjects of childbearing potential only. Serum pregnancy tests will be conducted at the following visits: Visit 1 (W0), ET, and Termination Visit. All other pregnancy tests will be urine dipstick. Baseline failures from SP0982 may have an additional urine pregnancy test at V1 of EP0012, at the investigator's discretion.
- s The C-SSRS will be completed for all subjects  $\geq 6$  years of age (see Section 10.4.3).
- t The Achenbach CBCL: CBCL/6-18 for children  $\geq 6$  years to <18 years of age; to be completed by the parent(s)/legal representative(s) (estimated completion time 45 minutes). For each version of the CBCL, subjects must have at least 1 year of data before transitioning to the next age range. The Achenbach CBCL should be completed by the same parent/legal representative, if possible (see Section 10.4.6).
- u The BRIEF should be used for subjects who are  $\geq 5$  years of age. For each developmentally appropriate version of the BRIEF, subjects must have at least 1 year of data before transitioning to the next age range (see Section 10.4.7).

**Table 5–3: Schedule of study assessments for Years 3 through 5 for EP0012 (Treatment Period, ET Visit, Termination Visit, and Unscheduled Visit for subjects ≥18 years at enrollment)**

	Treatment period a								End of Study period			Unscheduled b
Duration	Open-label: up to approximately 5 years								Up to 5 weeks			
Year of study	Year 3			Year 4		Year 5 +Extended Period						
Visit c	TC d	V12	V13	V14	V15	V16	V17	Vx e	ET Visit f	Term Visit g	LCM Solution Dispensation Visit	Unscheduled Visit
Week		118	142	166	190	214	238	X				NA
Concomitant medications and AED(s)	X	X	X	X	X	X	X	X	X	X		X
Laboratory tests h		X		X		X	X i	X i	X	X		
Pregnancy test j		X	X	X	X	X	X	X	X	X		
Dispense subject diary		X	X	X	X	X	X	X	X	X		
Subject diary return/review		X	X	X	X	X	X	X	X	X		X
Call IRT		X	X	X	X	X	X	X e	X	X		X
Dispense LCM		X	X	X	X	X	X	X	X	X	X	
LCM review/return		X	X	X	X	X	X	X	X	X	X	
Withdrawal criteria	X	X	X	X	X	X	X	X	X	X		X

AE reporting	X	X	X	X	X	X	X	X	X	X		X
--------------	---	---	---	---	---	---	---	---	---	---	--	---

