**8.1.4 Visits 12, 13, 14, 15, 16, 17 and X (Weeks 118, 142, 166, 190, 214, 238, and X, Years 3 to 5 + Extended Period)**

**8.1.4.1 Subjects  $< 18$  years**

The following tasks and procedures are to be performed at these visits (Visit X [Vx] visits are to be performed every 24 weeks):

- Concomitant medications and AEDs

- Physical examination (complete, Visit 13, 15, 17, and odd numbered visits thereafter)
- Neurological examination (brief, Visit 12, 14, 16, 17, and even numbered visits thereafter)
- ECG (12-lead) assessment (Visit 13, 15, 17, and odd numbered visits thereafter)
- Vital signs (pulse rate, BP) including orthostatic assessments
- Body weight and height (height at Visit 12, 14, 16, and even numbered visits thereafter)
- Tanner staging (will be performed only for subjects who are pubescent at Visit 1 or who enter puberty during the course of the study) (Visit 13, 15, 17, and odd numbered visits thereafter)
- C-SSRS assessment (for subjects  $\geq 6$  years of age)
- Blood and urine samples for clinical laboratory assessments (includes hematology, chemistry, and urinalysis) (laboratory tests are applicable for combined Visit 17/Termination Visit. If Visit 17 is not the Termination Visit, laboratory tests are not required. Laboratory tests are not performed at Visit 13 and 15 according to Protocol Amendment 3.
- Urine pregnancy test (for women of childbearing potential)
- Contact IRT
- Dispense subject diary
- Subject diary return/review
- Dispense LCM
- LCM review/return
- Assess withdrawal criteria
- AE reporting
- Achenbach CBCL for subjects  $\geq 6$  years to  $< 18$  years of age (Visit 13, 15, 17, and odd numbered visits thereafter)
- BRIEF for subjects  $\geq 5$  to  $< 18$  years of age (Visit 13, 15, 17, and odd numbered visits thereafter)

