#### **8.1.4.2 Subjects $\geq 18$ years**

The following tasks and procedures are to be performed at these visits, additional routine visits (Visit X) can be done after Visit 17 (Vx visits are to be performed every 24 weeks) with assessments described in [Table 5-3](#).

- Concomitant medications and AEDs
- Blood and urine samples for clinical laboratory assessments (includes hematology, chemistry, and urinalysis) (laboratory tests are applicable for combined Visit 17/Termination Visit. If Visit 17 is not the Termination Visit, laboratory tests are not

required. Laboratory tests are not performed at Visit 13 and 15 according to Protocol Amendment 3.

- Urine pregnancy test (for women of childbearing potential)
- Contact IRT
- Dispense subject diary
- Subject diary return/review
- Dispense LCM
- LCM review/return
- Assess withdrawal criteria
- AE reporting

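### Table 5-2 footnote f sends children's Visit X to the adult schedule, which lacks 9 of the 19 assessments marked there, and the weight cell conflicts with Section 8.1.4.1

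*Protocol*

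**What the plan says.** Section 5.2 of the Protocol assigns Table 5-2 to subjects under 18 at enrollment and Table 5-3 to adults; the latter's title ends "Unscheduled Visit for subjects ≥18 years at enrollment". Each table has a Visit X (Vx) column for the routine visits held every 24 weeks after Visit 17 (Week 238).

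Footnote f, attached to the Vx heading of Table 5-2, gives two instructions for these children: "Additional routine visits should be scheduled and performed in accordance with footnote 'b' to avoid visit window deviations", and "Assessments must be performed in accordance with Table 5-3".

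The procedure sections divide the visits by age. Section 8.1.4.1 (under 18) covers Visit X and gives the paediatric list with its odd and even rules. Section 8.1.4.2 (18 and over) is where the adult table, Table 5-3, is invoked: "additional routine visits (Visit X) can be done after Visit 17 (Vx visits are to be performed every 24 weeks) with assessments described in" that table.

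On weight and height, the Vx cell of Table 5-2 reads "X (even visits only" for the combined row. Section 8.1.4.1 has "Body weight and height (height at Visit 12, 14, 16, and even numbered visits thereafter", and footnote n to Table 5-2 has "Height will be recorded at Visits 12, 14, 16, Visit X (even visits), and at the ET and Termination Visit".

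**The concern.** Footnote f is worded as mandatory, yet it contradicts the column it annotates and the matching procedure section. A site that obeys it would run a child's Visit X on the adult list. That would drop ECG and vital signs, which feed two of the three secondary safety variables in Section 4.1.2. It would also drop the C-SSRS, on which withdrawal criterion 7 in Section 6.3 rests. A site that follows the column instead departs from the footnote.

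Footnote b, the other pointer, describes unscheduled visits, which are discretionary and have ECG and laboratory work only as needed. The 7-day window is in footnote c. Together the two wrong pointers make a required paediatric visit look optional and reduced.

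The weight cell is a separate conflict. Weight at odd Visit X visits is required by Section 8.1.4.1 and left out by the table. Children under 50 kg are dosed in mg/kg/day (Section 7.2.1, Table 7-1), so their weight also matters for treatment.

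Measurements not taken cannot be recovered at analysis.

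**Working it through.** No planned figure is involved, so the check compares the current schedules row by row and then applies the visit calendar.

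**Row counts at Visit X**

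- Table 5-2 has 20 rows. All but endocrinology are marked at Vx: 20 − 1 = 19.
- Table 5-3 has 10 rows, all marked at Vx: concomitant medication, laboratory tests, pregnancy test, diary dispensing, diary return, IRT, LCM dispensing, LCM return, withdrawal criteria and AE reporting. All 10 are among the 19.
- Missing from Table 5-3: 19 − 10 = 9.

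| Missing assessment | Table 5-2, Vx column |
|---|---|
| Vital signs; C-SSRS | every visit (2) |
| Brief neurological examination; weight and height | even visits (2) |
| Complete physical examination; ECG; Tanner; CBCL; BRIEF | odd visits (5) |

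Section 8.1.4.1 lists all nine for Visit X.

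**What a literal reading drops at each visit**

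Visit X visits are assumed to be numbered on from Visit 17, as the odd and even rules imply.

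- Visit 18: Week 238 + 24 = 262, even. Dropped: 2 + 2 = 4.
- Visit 19: Week 262 + 24 = 286, odd. Dropped: 2 + 5 = 7. This is a ceiling, because Tanner applies only to subjects in puberty, C-SSRS only from age 6, and CBCL and BRIEF stop at 18.

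**Could footnote f be meant only for those who have become adults?** No. The note under Table 5-2 keeps subjects who turn 18 on the paediatric schedule and excuses them only from CBCL and BRIEF.

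**Weight**

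| Visit | Section 8.1.4.1 | Table 5-2, Vx cell |
|---|---|---|
| 18 (Week 262) | weight | weight |
| 19 (Week 286) | weight | none |

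The row is marked at every visit from 12 to 17, so the restriction on weight begins only at Visit X. The mismatch first appears at Week 286, which is 286 × 7 / 365.25 = 5.48 years after Visit 1. It recurs every 2 × 24 = 48 weeks. Height is restricted to even visits in all three places and is consistent apart from footnote f.

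**How many children reach Visit X**

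Section 5.1.1 is not clear on this. One statement is "A Treatment Period lasting for at least 5 years (238 weeks) for the population less than 18 years old at enrollment", which allows Visit X. Another treats five years of participation as a limit. Five years is 5 × 365.25 / 7 = 260.9 weeks, so Visit 18 falls 262 − 260.9 = 1.1 weeks after that limit and Visit 19 falls 286 − 260.9 = 25.1 weeks after it.

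**The case against.** The best reply is that this is a slip the document corrects itself. The Vx column states what is done and when, Section 8.1.4.1 repeats it for children, and both Section 8.1.4.2 and the title of Table 5-3 reserve that table for adults. The rationale for Amendment 3 (Appendix 6) says the paediatric assessments after Week 94 were to be kept. A careful site would follow the column.

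The consequences are also limited. All nine assessments are marked at the Early Termination and Termination Visits in Table 5-2, which footnote f does not touch. Review of withdrawal criteria and AE reporting stay at Visit X even in Table 5-3. If five years is a ceiling, Visit 18 lies at the limit and Visit 19 never happens, so neither the weight mismatch nor the count of 7 would arise. A child aged 13 or more at entry would be over 18 by Visit 19 and would no longer need CBCL or BRIEF. The wrong letter for the window has little effect, since Section 8 repeats the 7-day window for all visits.

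These points stand as limits on reach. They do not remove the contradiction. The sponsor's intent can be inferred, but the instruction says the opposite in mandatory terms. The protocol created Visit X with its own paediatric rules, so it provides for such visits. End-of-treatment readings do not replace the interim ECG, vital signs and C-SSRS that Section 8.1.4.1 asks for.

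**Conclusion.** The point holds. Footnote f of Table 5-2 is a wrong cross-reference in mandatory wording. It points to a schedule lacking 9 of the 19 assessments marked at Visit X, amounting to 4 at Week 262 and up to 7 at Week 286. The reference to footnote b instead of footnote c is also wrong. The weight cell contradicts Section 8.1.4.1 and footnote n from Week 286 onward.

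The size depends on how many children remain after Week 238, which the Protocol does not state and which Section 5.1.1 leaves open. No endpoint definition or analysis set is affected. What is at risk is interim safety data in children late in follow-up, so the text should be corrected, although the design is sound.

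**What to change.** Make three wording corrections in Table 5-2:

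1. In footnote f, replace the reference to Table 5-3 with a reference to the Vx column of the same table.
2. In footnote f, replace footnote b with footnote c for the visit window.
3. In the Vx cell for body weight and height, limit only height to even visits, as in footnote n and Section 8.1.4.1.

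There is no design change. Relative to the present Vx cell, the cost is one extra weight measurement per child every 48 weeks. Relative to Section 8.1.4.1, nothing is added.

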**Table 5-4: Schedule of study assessments (Taper Period and Safety Follow-Up Period)**

Assessment	Taper Period a (up to 4 weeks)	Safety Follow-Up Period b	
	End of Taper Visit (maximum 3 days after the last dose) c	Safety Follow-Up Visit	Safety Follow-Up TC
		2 weeks (±2 days) after last dose of study drug	30 days (-1/+3 days) after last dose of study drug
Concomitant medications and AED(s)	X	X	X
Physical exam (complete)	X	X	
Neurological exam (brief)	X	X	
12-lead ECG d	X	X e	
Vital signs (BP and pulse) including orthostatic assessments	X	X	
Body weight	X	X	
Laboratory tests:			
Chemistry/hematology	X	X e	
Endocrinology		X e	
Urine pregnancy test f	X	X	
Contact IRT	X		
Subject diary return/review g	X		
LCM review/return	X		
Withdrawal criteria	X		
AE reporting	X	X	X
C-SSRS h	X	X	
Healthcare resource use i	X	X	
Work/school days lost due to epilepsy i	X	X	
Days with help from a caregiver due to epilepsy i	X	X	

AE=adverse event; AED=antiepileptic drug; BP=blood pressure; C-SSRS=Columbia-Suicide Severity Rating Scale; ECG=electrocardiogram; IRT=interactive response technology; LCM=lacosamide; TC=telephone contact

Note: The schedule of study assessments for the Taper Period and Safety Follow-Up Visit includes some of the subjects who tapered in SP0982 after the 125th event who consented to enter EP0012 for the Safety Follow-Up only.

a Subjects who will not continue on LCM must complete an End of Taper Visit and a Safety Follow-Up Period; see Table 5-4. For subjects who continue on commercial LCM, the (Early) Termination Visit is the last visit in the study.

- b There will be a 30-day (-1/+3 days) Safety Follow-Up Period for subjects who complete the End of Taper Visit. The Safety Follow-Up Period consists of a clinic visit 2 weeks after the End of Taper Visit followed 2 weeks later by a TC Visit.
- c An End of Taper Visit will be scheduled at the end of the Taper Period (up to 4 weeks) depending on dose level achieved; see [Table 7-2](#). Of note, for subjects who enter the Taper Period at  $\leq 2$ mg/kg/day (oral solution) or 100mg/day (tablets), the End of Taper Visit will take place at the ET or Termination Visit.
- d The ECG recordings should be performed at the same time of day (when possible) and prior to blood sample collection and vital sign assessments. Care should be taken to assure proper lead placement and quality ECG recordings. If possible, subjects should rest in a supine position at least 5 minutes prior to each recording and should be motionless during the recording. In pediatric subjects (<18 years of age) a 12-lead ECG (2 interpretable recordings) approximately 20 to 30 minutes apart must be performed.
- e The assessment will only be required for subjects with an abnormal value (clinical chemistry, hematology, or endocrinology) or reading (ECG) at the previous clinic visit.
- f Pregnancy tests will be performed for female subjects of childbearing potential only. A urine pregnancy test will be performed.
- g The last subject diary will be returned at the End of Taper Visit.
- h The C-SSRS will be completed for all subjects  $\geq 6$  years of age (see [Section 10.4.3](#)).
- i Healthcare resource use, work/schools days lost due to epilepsy, and days with help from a caregiver due to epilepsy will be assessed only for patients completing the study after  $\leq 2$  years. These assessments are not applicable for patients tapering down or performing the SFU-visits during Years 3, 4 or 5).

